F.1.6. Schedule of administration during treatment phase: At the baseline visit, women who successfully complete the run-in with 0.1 mg/hr NTG and meet all eligibility criteria will be assigned in a 1:1 ratio to start using a 0.2 mg/hr NTG or identical-appearing placebo patch for the treatment phase of the study. Women will again apply a new patch each night, directly after removing the old one, and avoiding patch-free episodes that could interfere with maintenance of nitrate tolerance. At a 1-week follow-up visit, those who report persistent hot flashes, do not have blood pressure <90/60 or >180/110, and pose no other major safety or tolerability issue will have their NTG (or placebo) dose increased to 0.4 mg/hr. Based on the 2-week follow-up visit, women with persistent hot flashes and no significant blood pressure, safety, or tolerability issue will have their dose increased to 0.6 mg/hr and remain at this for the remainder of the study. Women who report being completely satisfied on a dose lower than 0.6 mg/hr or who have major safety or tolerability issues will be permitted to remain on a lower dose.

F.1.7. Discontinuation of NTG/placebo after treatment phase: At the 12-week visit, participants will be asked to wean off NTG (or placebo) over the next 1 to 3 days, by decreasing their patch dose on a nightly basis before stopping NTG/placebo completely. Specifically, participants who are being weaned from the 0.6 mg dose of study medication will be instructed to switch to 0.4 mg for one day, then to 0.2 mg for one day, then to stop study drug altogether. Participants who are being weaned from the 0.4 mg dose will switch to 0.2 mg for one day before stopping medication altogether. Women who are taking the 0.2 mg (the lowest dose hypothesized to have a therapeutic effect) will simply stop study medication without any change in dose. Women will be given a last supply of NTG or placebo medication (one patch of each dose strength needed to complete the weaning). Participant and staff blinding will be maintained throughout the weaning process; for participants taking placebo, weaning will use placebo rather than active NTG patches. In the event that a participant develops a potentially severe adverse event such as chest pain during weaning, she will be directed to seek immediate emergency attention, just as she would during any other time point of the study.

F.2 Concomitant Interventions

F.2.1 Allowed interventions

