Every effort will be made to assure that participants complete follow-up procedures and visits according to the study protocol. Participant contact information including address, phone number(s), fax number(s), and email address will be obtained at the Screening Clinic Visit. Study coordinators will also request contact information for two family members or friends who will be able to locate the participant. The study team will encourage retention by educating participants about the importance of the study, maintaining a friendly and efficient study clinic environment, and encouraging excellent staff-participant rapport. Participants who miss a visit will be contacted by the study coordinator to reschedule the visit and to provide assistance in completing the visit. Participants will also be offered gift cards with the return of each completed hot flash diary (\$25 at the Baseline Clinic Visit and 5-Week Clinic Visit, and \$50 at the 12-Week Clinic Visit).

H.2.8 Follow-up visit time windows

Suggested time windows for completion each of the post-randomization follow-up evaluations will be as follows:

| Follow-Up Assessment | Time Window |
|----------------------|-------------|
|----------------------|-------------|

| | |
|--|--|
| 1-week clinic visit | 7 (\pm 3) days after the baseline clinic visit (i.e., 4 to 10 days after the baseline visit) |
| 2-week clinic visit | 14 (\pm 3) days after the baseline clinic visit (i.e., 11 to 17 days after the baseline visit) |
| 3-week telephone call | 21 (\pm 3) days after the baseline clinic visit (i.e., 18 to 24 days after the baseline visit) |
| 5-week clinic visit | 5 weeks (\pm 6 days) after the baseline clinic visit (i.e., 29 to 41 days after the baseline visit) |
| 8-week telephone call | 8 weeks (\pm 6 days) after the baseline clinic visit (i.e., 49 to 63 days after the baseline visit) |
| 12-week clinic visit | 12 weeks (\pm 6 days) after the baseline clinic visit (i.e., 78 to 90 days after the baseline clinic visit) |
| 4-week post-discontinuation telephone call | 28 to 42 days after the 12-week clinic visit (or discontinuation of study medication) |

I. SAFETY ASSESSMENTS

I.1 Potential Risks and Protective Measures

I.1.1 Potential risks of study procedures

A. Potential risks associated with the therapeutic intervention (transdermal NTG) include:

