Study medication may be discontinued if deemed necessary to protect the safety of a participant or preserve the integrity of the study. The decision to discontinue study medication will be made on a case-by-case by the principal investigator, with input from the steering committee and the DSMB as needed. In most cases, discontinuation of study medication will prompt early termination of study participation, although there may be select cases where study medications are discontinued only temporarily, and the participant is subsequently restarted on study medication and then followed for the full duration of the study.

Specific reasons for discontinuation of study medication and/or early termination of the study include: 1) syncopal episode attributable to NTG-induced hypotension or vasodilation; 2) development of persistent blood pressure <90/60, blood pressure <100/60 with symptoms of dizziness, or orthostatic blood pressure with symptoms of dizziness, which do not resolve with reduction in study medication dose; 3) development of persistent severe hypertension defined by blood pressure >180/110; 4) development of pregnancy or decision to try to become pregnant (among women who are not yet postmenopausal); 5) development of another clinically significant adverse event limiting a participant's ability to safely continue to use the study drug; 6) unusually disruptive behavior exhibited by a participant during study visits that endangers the safety or well-being of the participant or study staff; or 7) decision to terminate the study by the IRB, the NIA, or other regulatory bodies.

Participants may also withdraw voluntarily from participation in the study at any time and for any reason. If a participant decides to discontinue the study drug or withdraw from the study, the study coordinator will try to elicit the reason for this decision. The coordinator may also try to trouble-shoot participant concerns or discuss strategies for overcoming barriers to continued participation in the study in order to try to retain the participant, provided that the decision to terminate is not driven by a safety issue.

J.2 Discontinuation/Termination Procedures

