To assess tolerability and safety of NTG, we will compare group-specific rates of: 1) severe symptoms that are potentially attributable to NTG therapy (i.e., headache limiting activities of daily living, chest pain or tightness limiting activities of daily living, or syncope/fainting); and 2) any adverse events with a severity rating of 3 or higher on the CTCAE severity scale (National Cancer Institute 2009). We will also examine group-specific rates of all adverse events, regardless of severity and of anticipated relationship to NTG therapy. Inferences for rare outcomes will be obtained using Fisher's exact test. Because intention-to-treat analysis is conservative, any suggestive differences in safety outcome rates will be assessed accounting for adherence, final dose, and their interactions with treatment.

K.3 Sample Size Determination

Sample size calculations are based on parameter estimates from prior pharmacologic hot flash trials conducted by the investigators such as the FAST(Grady, Cohen et al. 2007) and CHIMES trials (Grady, Sawaya et al. 2009), which had similar eligibility criteria with respect to age, hot flashes, and treatment history. We assume the study sample will be characterized by: a) mean baseline hot flash frequency of >9 hot flashes/day; b) mean reduction in hot flash frequency in the control group of <3 hot flashes/day (i.e., <33%); c) standard deviation of change in hot flash frequency of ~4.5 hot flashes per day; and d) correlation between baseline and follow-up values of ~0.55.

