Under these assumptions, a sample size of 140 (70 per group) should provide an estimated 87% power in 2-sided tests with type-I error of 5% to detect an 20% greater reduction in hot flash frequency (or 1.8 hot flashes per day) in the active treatment arm relative to the control arm. This will correspond to a 50-55% decrease in hot flash frequency from baseline in the active treatment group, which has previously been described as a clinically important effect in prior hot flash research (Butt, Deng et al. 2007). Estimates account for correlation of the repeated measures and loss to follow-up of up to 15%, and indicate that power will remain $\geq 80\%$ even if actual effect size or other parameters are less favorable than expected. This sample of 70 per group will also provide $>80\%$ power in 2-sided tests with type-I error of 5% to detect a between-group difference in mean frequency of moderate-to-severe hot flashes of ~ 1.5 hot flashes per day, as well as ~ 3.3 points in hot flash severity scores.

K.4 Additional Statistical Considerations

K.4.1 Drop-out rates

Based on past experience, participant dropout levels are expected to remain under 15% over 12 weeks. The assumption of non-informative dropout will be examined by comparing the baseline characteristics and early post-randomization outcomes of participants who are lost to follow-up versus retained in the study. If drop-out rates differ substantially between groups, analyses will be adjusted for baseline covariates associated with retention. In sensitivity analyses, we will also use multiple imputation of missing outcomes under plausible informative missingness assumptions, along with standard methods for calculating summary estimates and confidence intervals, to assess the potential impact of loss to follow-up on treatment effect estimates (Schafer 1999).

K.4.2 Dose effects

In the event that an overall treatment benefit is detected over 12 weeks, we will conduct exploratory analyses to probe for differences in the magnitude of treatment effects by highest-achieved NTG dose, by testing for interaction between treatment assignment and highest-achieved NTG dose in a linear mixed model for change in hot flash frequency. This analysis will control for the main effect of highest achieved dose to control the placebo effect of this self-selected variable, as well as baseline factors that may confound it, such as age, body mass index, and baseline hot flash frequency or severity.

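### K.2.4 compares adverse-event rates by arm without allowing for follow-up that ends soon after the patch is stopped; if stopping differs by arm, the arm with more stopping would show fewer background or late events

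*Combined protocol and SAP*

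**What the plan says.** Coordinators ask about adverse events at every contact after study medication begins. The last contact is a telephone call, and H.2.8 times it at "28 to 42 days after the 12-week clinic visit (or discontinuation of study medication"; item G of H.2.5 gives the same anchor with a 28-day minimum. J.1 adds: "In most cases, discontinuation of study medication will prompt early termination of study participation". It allows that some women may restart and be followed to the end. Under J.2, staff attempt the final call after early stopping; its completion is not assured.

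K.2.4 compares group-specific rates of limiting headache, limiting chest pain, syncope and events of CTCAE grade 3 or higher. It then widens the scope: "We will also examine group-specific rates of all adverse events, regardless of severity and of anticipated relationship to NTG therapy". On method it says: "Inferences for rare outcomes will be obtained using Fisher's exact test". It names no method for commoner events and does not say whether a rate is per woman or per unit of time. It remarks that intention-to-treat analysis is conservative for safety and plans a further look by adherence and final dose if a suggestive difference appears. K.4.1 provides for covariate adjustment if dropout differs by arm, and for multiple imputation of missing outcomes.

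**The concern.** The observation window for harms is set by when a woman stops the patch, not by randomization. A comparison of the proportions of women with an event treats a short window and a full one as equal, and a woman whose contact has ended appears as event-free. If one arm has more early stopping, it has less time in which to record background or late events.

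Hypothesis 4 expects no significant difference in chest pain, syncope or grade 3+ events. If stopping were commoner on NTG, the shortfall would lean towards that conclusion; if commoner on placebo, it would lean the other way. In either case the reader of the results could not tell how much of a difference, or of its absence, came from unequal follow-up.

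**Working it through.** **The plan's own figures.** The documents give no power, event rate or precision for the safety comparison. Their one related figure is the 87% power for the primary outcome in K.3. It reproduces approximately: common SD 4.5/√(2(1 − 0.55)) = 4.74; baseline-adjusted SD 4.74 × √(1 − 0.55²) = 3.96; average of two follow-ups, assuming that they too correlate 0.55, 3.26; with 70 × 0.85 = 59.5 per arm and a difference of 1.8, power is 85%. This has no bearing on the harms comparison.

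**Inputs.** From the documents: 12 weeks of treatment, a final call 4 to 6 weeks later (H.2.8), 70 women per arm, and dropout under 15% overall (K.3, K.4.1). Assumed, because the documents do not give them: stopping by arm (20%/10% or 25%/5%, both averaging 15%), stopping at week 2, the background risk, and a constant hazard equal in both arms.

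**Window per woman.** Completer: W = 12 + 4 = 16 to 12 + 6 = 18 weeks. Stopper at week 2: w = 2 + 4 = 6 to 2 + 6 = 8 weeks, which is 38% (6/16) to 44% (8/18) of the completer's window.

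**Follow-up per arm.** Mean follow-up = (1 − d)W + d·w, where d is the proportion stopping.
- 20%/10%: 14.0 v 15.0 weeks (W = 16) or 16.0 v 17.0 (W = 18), so 6% to 7% less in the arm with more stopping.
- 25%/5%: 13.5 v 15.5 or 15.5 v 17.5, so 11% to 13% less.
- 15%/15%: no difference.

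**Apparent difference under equal hazards.** If a completer's risk is P, a stopper's is 1 − (1 − P)^(w/W). The observed proportion in an arm is (1 − d)P + d[1 − (1 − P)^(w/W)]. The difference between arms is therefore −(d₁ − d₂) × {P − [1 − (1 − P)^(w/W)]}, where arm 1 has more stopping.

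Example, P = 0.5 and W = 16: the stopper's risk is 1 − 0.5^0.375 = 0.229. At 25%/5% the arms show 43.2% and 48.6%, a difference of −5.4 points.

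| Completer's risk P | W (weeks) | 20%/10% | 25%/5% |
|---|---|---|---|
| 50% | 16 | −2.7 | −5.4 |
| 50% | 18 | −2.3 | −4.7 |
| 10% | 16 | −0.6 | −1.2 |
| 10% | 18 | −0.5 | −1.1 |
| 5% | 16 | −0.3 | −0.6 |
| 5% | 18 | −0.3 | −0.5 |

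(Percentage points.)

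At a 10% background and 25%/5%, the largest entry is 0.0123 × 70 = 0.9 woman. At a 50% background the largest is 0.054 × 70 = 3.8 women, to be set against a standard error of √(2 × 0.25/70) = 8.5 points.

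**Do the other provisions correct this?** The adherence and final-dose analysis runs only if the crude comparison already looks suggestive, and it does not use observation time. Adjusting for baseline covariates does not equalise windows, and Fisher's test takes no covariates. Nothing in K.2.4 or K.4.1 classes the time after a woman's last contact as a missing safety outcome, so imputation is not clearly engaged.

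**The case against.** A reader might infer that NTG will drive more women off the patch and so will look falsely safe. The documents do not establish this. The two pilot women who stopped for headache were on the initial 0.1 mg/hr patch (C.3). Here every woman takes that dose in a run-in before randomization, and those who do not tolerate it are not randomized (F.1.5). None of the 17 pilot women who tolerated it stopped for side effects. I.1.2 speaks of decreasing or stopping, and J.1 lists low blood pressure as a reason to discontinue only if it does not resolve with dose reduction. Equally, 0 of 17 does not prove the opposite: its one-sided exact 95% upper bound is 1 − 0.05^(1/17) = 16%, from a study with four weeks of treatment.

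A second tempting inference is that the larger figures apply to Fisher's test and to Hypothesis 4. They do not. Fisher's test is named for rare outcomes only, and for these the shortfall is under one woman per 70 on the assumptions used. The differences of several points concern common events, for which no test is named and a person-time rate is not excluded.

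The lost time is also off drug. Treatment plus at least 28 days is covered if the call is completed, the plasma half-life after patch removal is about one hour (F.1.1), and headache is most frequent in the first 24 hours (I.1.1). Whether background events more than four weeks after the last patch belong in the comparison is partly a choice of estimand.

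All of this stands and limits the size of the point. It does not remove the gap: K.2.4 has not made that choice, and its denominator and window remain undefined.

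**Conclusion.** The point holds in a conditional form. Follow-up for harms depends on when a woman stops, and K.2.4 has neither a common window nor an adjustment for follow-up time. If stopping is unequal, the arm with more of it would show fewer background or late events. Under assumed week-2 stopping of 20%/10% to 25%/5% and a constant, equal hazard, the apparent difference is roughly −2 to −5 points at a 50% background, about −0.6 to −1.2 points at 10% with a 16-week window (slightly less with 18), and smaller for rarer events. It is zero if stopping is balanced. Later stopping shrinks it; a missed final call enlarges it. Early headache and events that themselves cause stopping are not lost. This is an inexpensive improvement to the safety analysis, not evidence that the planned comparison will mislead.

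**What to change.** In K.2.4:

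1. State the denominator and window for each adverse-event rate, and report adverse-event follow-up time by arm.
2. Run Fisher's comparison on events with onset in a fixed window from randomization that nearly all women complete, for example to day 35. A woman who stops at day 7 or later and completes the 28-day call is covered (7 + 28 = 35).
3. Add cumulative incidence of the first event, with censoring at the last completed adverse-event contact.
4. For all adverse events and for grade 3+ events, give exposure-adjusted rates as a supplement.

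Extra calls to early stoppers are not needed. Calls at weeks 8 and 12 alone would not create a shared window, because completers are followed to weeks 16 to 18. If such calls are offered as an option, the comparison that uses them should be truncated at week 12 in both arms.

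The cost is analysis-plan wording and a little more analysis, since onset and contact dates are already recorded. The censored and person-time analyses assume non-informative censoring, which is doubtful when a woman stops because of an event. Person-time rates also assume a roughly constant hazard, which does not suit headache concentrated in the first day. That is why the fixed-window comparison should stand beside them. The wording should be settled before unblinding.

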To evaluate the efficacy, safety, and tolerability of uninterrupted transdermal NTG therapy for menopausal hot flashes.

Design

Randomized, double-blinded, parallel-group, placebo-controlled trial of uninterrupted transdermal NTG therapy in peri- or postmenopausal women with hot flashes.

Interventions

Random assignment to uninterrupted daily use of transdermal NTG patches (participant-directed dose escalation from 0.2 to 0.6 mg/hr) for 12 weeks, versus uninterrupted daily use of identical-appearing placebo patches for 12 weeks.

Population

Women aged 40 to 62 years who are postmenopausal or in the late menopausal transition, document an average of at least 7 hot flashes per day, do not have coronary disease or multiple risk factors for coronary disease, and do not have contraindications to transdermal NTG therapy, recruited from the San Francisco Bay Area.

Outcomes

The primary outcome is change in the average frequency of any hot flashes from baseline to 4 and 12 weeks as documented by symptom diaries. Secondary efficacy outcomes include changes in frequency of moderate-to-severity hot flashes and total hot flash severity score from baseline to 4 and 12 weeks of treatment, also documented by symptom diaries. Additional secondary efficacy outcomes include changes in sleep quality, anxiety and depression symptoms, and menopause-related quality of life from baseline to 4 and 12 weeks of treatment, assessed using validated questionnaires. Additional safety outcomes include rates of severe headache, chest pain, and syncope, as well as other adverse events with a Common Terminology for Adverse Event Criteria severity grade of 3 or higher.

B. STUDY OBJECTIVES

B.1 Primary Objective

To determine the efficacy of uninterrupted transdermal NTG therapy in reducing the frequency of hot flashes in peri- and postmenopausal women.

We hypothesize that, compared to placebo, uninterrupted use of NTG will result in at least a 20% greater decrease in frequency of hot flashes (assessed by validated 7-day symptom diaries) over 12 weeks.

B.2 Secondary Objectives

A. To evaluate the efficacy of uninterrupted transdermal NTG therapy in reducing the severity of hot flashes in peri- and postmenopausal women.

We hypothesize that, compared to placebo, uninterrupted use of NTG will result in significant improvements in frequency of moderate-to-severe hot flashes and in cumulative hot flash severity score (assessed by validated 7-day symptom diaries) over 12 weeks.

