- Two resting blood pressure and heart rate measurements and orthostatic measurements will be obtained by a trained study coordinator during an in-person visit, or participants will be guided by the coordinator in obtaining these measurements at home during a video visit.
- Women who report no symptoms of hypotension or other safety issues, have blood pressures within acceptable parameters, and continue to report bothersome hot flashes will be asked to increase to the next higher dose patch (0.6 mg/hr for those previously on 0.4 mg/hr, or 0.4 for those previously on 0.2 mg/hr) or corresponding placebo. Those who are not eligible or who decline to increase their dose will be permitted to remain on a lower dose.
- Women who are not yet postmenopausal will be reminded to refrain from sexual activity or use barrier contraceptives; those who report unprotected sexual activity will be asked to provide a urine sample for pregnancy testing.
- Participants will be given a second hot flash diary and asked to record all hot flashes during the 7 days prior to their 5-Week Clinic Visit.
- An appropriate supply of study medication (or placebo) will be dispensed and participants will be asked to apply NTG or placebo patches on a nightly basis leading up to the 5-Week Clinic Visit

C. 3-Week Telephone Call (for women taking 0.6 mg/hr NTG (or placebo)

- If a participant was started on 0.6 mg/hr NTG (or placebo) at the 2-Week Clinic Visit, the study coordinator will call the participant 1 week later to discuss adherence, assess adverse events, and address questions.
- If a safety concern is raised by this call, the participant will be asked to come in immediately for an in-person or video-based visit (or directed to seek emergency medical attention, as appropriate)
- Participants will be reminded of when to start their next hot flash diary at least 7 days before the 5-Week Clinic Visit.

D. 5-Week Clinic Visit

- Approximately 5 weeks after randomization, women will have a follow-up visit, returning their study medication logs and any unused medication, as well as their second completed hot flash diary.
- Potentially severe side effects of NTG will be systematically assessed and recorded, and other unanticipated adverse events that are reported will also be documented according to standard protocols.
- Study coordinators will review medication diaries and tabulate unused patches to assess adherence and trouble-shoot barriers to adherence.

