Urine pregnancy testing: There are no direct risks associated with urine pregnancy testing, although participants may experience this as inconvenient or unpleasant.

Electrocardiography (ECG) testing: It is possible for participants to develop a mild rash where the ECG electrodes are attached, but this rash usually resolves without treatment.

I.1.2 Protections against risks

A. Protections against potential risks of uninterrupted transdermal NTG therapy:

Headache: To reduce headache, women reporting a history of more than two headaches per month that interfere with their daily activities, or taking prescription medication to prevent or treat headache in the past month, will be excluded from participating in this study. Women reporting heavy alcohol use that could increase their risk of headache and who are uncomfortable decreasing their alcohol intake during the study will also be excluded. Women who develop significant headache during the brief run-in period with the 0.1 mg/hr NTG patch will also be excluded before randomization. Prior to administration of either nitroglycerin or placebo, women will be given handouts describing simple over-the-counter headache remedies, including acetaminophen (Tylenol) and ibuprofen (Motrin), as tolerated. At follow-up visits, transdermal NTG therapy may be decreased or stopped in women reporting headache associated with therapy that interferes with daily activities. Study staff will instruct participants who experience persistent headache that is not attributable to NTG therapy to seek further evaluation and treatment from their regular source of health care.

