At all on-treatment interim follow-up visits (i.e., 1-week, 2-week, 5-week), transdermal NTG will be decreased or stopped in women with blood pressures <90/60 mm Hg (both measurements), or in those with blood pressures <100/60 mm Hg and symptoms such as dizziness that are suggestive of hypotension. Study medication will also be decreased or stopped in women with symptoms such as dizziness who have a resting blood pressure in the normal range but demonstrate orthostatic changes in blood pressure or heart rate when rising from the supine to standing position. These

women will also be given a standardized letter documenting their blood pressure reading to take to their regular health care provider to promote further monitoring and/or evaluation. In the event that there is a concern about the reliability of clinic measurements, or women report symptoms suggestive of hypotension despite having blood pressure measurements in the normal range, home-based or ambulatory blood pressure measurements will be obtained, to detect episodes of hypotension that may have been missed by clinic measurements. In the (hopefully unlikely) event that a participant reports a recent episode of syncope or loss of consciousness, study staff will also urge the participant to seek emergency medical attention.

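### K.2.4's conditional safety follow-up accounts for final dose, which the events being analysed help to set, so its dose results can mislead; the randomised arm comparison is not affected

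*Combined protocol and SAP*

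**What the plan says.** K.2.4 first compares rates by randomised group, with Fisher's exact test for rare outcomes. It then adds that "any suggestive differences in safety outcome rates will be assessed accounting for adherence, final dose, and their interactions with treatment". It names no effect scale for this step and no rule linking dose to the time of the event.

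Other sections let the events act on the dose:

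- I.1.2, headache: "transdermal NTG therapy may be decreased or stopped in women reporting headache associated with therapy that interferes with daily activities".
- I.1.2, hypotension: "Study medication will also be decreased or stopped in women with symptoms such as dizziness" when resting pressure is normal but there are orthostatic changes. Low readings have the same consequence.
- J.1 lists as a reason for stopping a "syncopal episode attributable to NTG-induced hypotension or vasodilation".
- F.1.6 lets two kinds of women stay on a lower dose: "Women who report being completely satisfied on a dose lower than 0.6 mg/hr or who have major safety or tolerability issues".
- H.2.5, 2-week visit: "Those who are not eligible or who decline to increase their dose will be permitted to remain on a lower dose".

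K.4.2 treats the efficacy question with more care. It uses highest-achieved dose, recognises that participants select it, adjusts for baseline confounders and labels the analysis exploratory. K.2.4 uses final dose, which can fall after an event, and states none of these safeguards.

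**The concern.** Activity-limiting headache and syncope are named K.2.4 outcomes, and both can determine the final dose. Low blood pressure and dizziness are not named there. They enter through the tabulation of all adverse events or as grade 3 and above. Women with events are therefore moved into the lower final-dose groups, and the 0.6 mg/hr group is cleared of some of them.

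Placebo women are titrated in the same way, so the treatment interaction compares like with like if both arms respond alike. They may not. B.1 expects that "uninterrupted use of NTG will result in at least a 20% greater decrease in frequency of hot flashes". If so, more NTG women should hold at a low dose because they are satisfied. Blood-pressure triggers may also fire more often on NTG. These two routes push the dose pattern in opposite directions.

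At stake is the explanation of an arm difference. A report could say that risk falls with dose, or rises more steeply than it does, when the pattern comes from who was held, stepped down or stopped.

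**Working it through.** K.2.4 gives no figure to reproduce, so the check is a worked illustration.

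**Inputs**

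- First-week event risk at each dose step (assumed): flat, 10% NTG v 3% placebo; rising, 5/10/15% v 3%.
- p, the chance that an event changes dose (assumed). At 0.2 mg/hr the woman stays classed at 0.2. At 0.4 and 0.6, 70% step down one level and 30% stop, classed by the last dose worn.
- Holds for satisfaction: h1 = 3/17 at 0.2 and h2 = 3/14 at 0.4, from the pilot's 3/3/11 of 17 women ending at 0.2/0.4/0.6 (C.3). C.3 gives no reasons, so reading these as satisfaction is an assumption. Placebo holds at the same rate, or at a third of it (1/17, 1/14).

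**Benchmark** (every woman taken to the dose whatever her events): risk = 1 − product of (1 − r).

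- Flat, NTG: 10.0/19.0/27.1%. Placebo: 3.0/5.9/8.7%. Risk difference (RD) 7.0/13.1/18.4 points; odds ratio (OR) 3.59/3.73/3.89.
- Rising, NTG: 5.0/14.5/27.3%. RD 2.0/8.6/18.6; OR 1.70/2.70/3.93.

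**Formulas by final dose**, with r1, r2, r3 the risks at the three steps:

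- Reach 0.4: a = (1 − r1p)(1 − h1). Reach 0.6: b = a(1 − r2p)(1 − h2).
- All ending at 0.2: r1p + (1 − r1p)h1 + 0.7·a·r2p.
- All ending at 0.4: 0.3·a·r2p + a(1 − r2p)h2 + 0.7·b·r3p.
- All ending at 0.6: b(1 − 0.7·r3p).
- No event: (1 − r1)h1; (1 − r1)(1 − r2)(1 − h1)h2; (1 − r1)(1 − r2)(1 − r3)(1 − h1)(1 − h2).
- With event = all ending there − no event.

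**Flat risk, equal rules, p = 0.5.** NTG: rp = 0.05, a = 0.95 × 14/17 = 0.7824, b = 0.7824 × 0.95 × 11/14 = 0.5840. All ending at 0.2: 0.0500 + 0.1676 + 0.0274 = 0.2450. No event: 0.9 × 3/17 = 0.1588. Event: 0.0862. The other cells follow in the same way.

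| Final dose | NTG event / none | Placebo event / none | Risk | RD | OR |
|---|---|---|---|---|---|
| 0.2 | 0.0862 / 0.1588 | 0.0262 / 0.1712 | 35.2% v 13.3% | 21.9 | 3.55 |
| 0.4 | 0.0485 / 0.1429 | 0.0154 / 0.1660 | 25.3% v 8.5% | 16.8 | 3.65 |
| 0.6 | 0.0918 / 0.4717 | 0.0306 / 0.5906 | 16.3% v 4.9% | 11.4 | 3.75 |

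**All scenarios, final dose 0.2/0.4/0.6**

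| Scenario | OR | RD (points) |
|---|---|---|
| Flat: benchmark | 3.59/3.73/3.89 | 7.0/13.1/18.4 |
| Equal rules, p = 0.10 | 3.59/3.74/3.86 | 11.3/14.1/17.1 |
| Equal rules, p = 0.25 | 3.58/3.72/3.82 | 16.3/15.3/15.1 |
| Equal rules, p = 0.50 | 3.55/3.65/3.75 | 21.9/16.8/11.4 |
| p = 0.6 NTG v 0.3 placebo | 6.01/4.39/2.33 | 29.1/18.8/7.4 |
| Unequal holds, p = 0.50 | 1.21/1.43/3.75 | 4.2/6.1/11.4 |
| 0.6 v 0.3 and unequal holds | 2.22/2.11/2.33 | 16.5/11.8/7.4 |
| Rising: benchmark | 1.70/2.70/3.93 | 2.0/8.6/18.6 |
| Equal rules, p = 0.50 | 2.24/4.00/4.00 | 12.3/18.6/12.3 |
| Unequal holds, p = 0.50 | 0.76/1.56/4.00 | −5.4/7.9/12.3 |
| 0.6 v 0.3 and unequal holds | 1.42/2.41/2.53 | 6.6/14.5/8.5 |

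With equal rules the OR stays close to benchmark under flat risk, and less close at the two lower doses under rising risk. The RD pattern reverses under flat risk once enough events change dose.

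**Dose at onset.** In this model the first-week risk among all women wearing a dose is r itself, so the table returns 10/10/10% or 5/10/15% on NTG and 3/3/3% on placebo, whatever the feedback.

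**The case against.** The case against is substantial.

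- **Reach.** Only a conditional follow-up is affected. A reader might infer that the trial's safety conclusion is biased. It is not: K.2.4 compares the randomised groups first, and Hypothesis 4 concerns that comparison.
- **Existing safeguard.** Placebo is titrated by the same rules under blinding, and the interaction is planned. On the OR scale with equal rules this works well under flat risk. The RD reversal needs many events to change dose.
- **Cancellation.** The large OR gradients come from switching on one arm difference at a time. With both, the OR shows no false gradient under flat risk, although its level is too low, and only attenuation under rising risk. A reader might infer that the follow-up will report a reversed gradient. The documents do not support that.
- **Inputs.** The split of 60% v 30% is weakly supported, since more frequent blood-pressure triggers are not the same as a higher chance of dose change given an event. Headache only may change the dose. A risk of 10% at three steps is 1 − 0.9³ = 27% cumulative, high for activity-limiting events. The pilot's 37% (I.1.1) was for any headache.
- **Sparse data.** With 70 per arm and 60% v 30%, the 0.2 group holds about 18 v 13 women. In 4,000 simulated trials an approximate Wald test of the 0.6-v-0.2 interaction reached p < 0.05 in about 4%. A misleading claim would more likely be descriptive than significant.
- **Meaning of final dose.** F.1.7 says that "participants who are being weaned from the 0.6 mg dose of study medication will be instructed to switch to 0.4 mg for one day", and then to 0.2, so a reader might infer that every completer's final dose is 0.2. F.1.7 places weaning after the treatment phase, so the natural reading is the last treatment-phase dose.

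These points limit the size. They do not remove the fault: the plan explains events by a variable that the events can change, on an unstated scale.

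**Conclusion.** The point holds for the conditional follow-up only and is worth a wording change. The link from event to dose is explicit in I.1.2, J.1, F.1.6 and H.2.5. Direction and size depend on the scale, on the share of events that change dose, and on whether the arms hold or step down at different rates. All these inputs are assumed, apart from the pilot's dose split, so the figures show what can happen and do not forecast it.

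Overall adherence could have the same problem if women stop patches after an event. A reader might take that as established. It is inferred: F.3.3 does not say whether patches after a self-chosen stop still count as recommended, so no size is given here.

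**What to change.** Keep the randomised comparison as the safety inference. In K.2.4, replace the end of the sentence, from the word assessed onward, with:

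> described, as exploratory analyses in both arms, by the dose of the last patch applied before event onset (first week at that dose and later weeks separately, with women or participant-weeks at that dose as denominator and exact 95% intervals) and by adherence up to the day before onset. Events on a dose-change day will be shown under both assignments, and events during weaning separately. Any table by final treatment-phase dose or overall adherence will state its scale and note that events may have caused the dose or adherence level.

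The data are already planned: onset date (G.1.3), dispensed dose (F.1.3), and date and time of each patch (F.3.1). No change to the adverse event form is needed.

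The cost is modest programming and sparse cells. Under flat risk and p = 0.5, expected first-week NTG events per 70 women are 70 × 0.10 × (1, 0.7824, 0.5840) = 7.0/5.5/4.1. On placebo they are 70 × 0.03 × (1, 0.8112, 0.6278) = 2.1/1.7/1.3. Some bias remains if women differ in susceptibility. With an assumed gamma frailty of variance 1, true first-week rates of 10/10/10% and 5/10/15% appear as 10.0/9.6/9.0% and 5.0/9.6/13.8%.
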